3.3 Patient enrollment and randomization

Investigators should keep a record, the patient screening log, of patients who entered pre-study screening.

The investigators will:

1. Obtain signed informed consent from the potential patient before any study specific procedures are performed.
2. Assign potential patient a unique enrollment number, beginning with 'E#'.
3. Determine patient eligibility in accordance with inclusion/exclusion criteria.
4. The Interactive Voice Response System/Interactive Web Response System (IVRS/IWRS) will assign an eligible patient unique randomization code (patient number), beginning with "#".

As patients are enrolled for the study, they must be allocated an E-code via IVRS. The E-code is a 7-digit number made up of the center number and the patient number within that particular center.

If a patient withdraws from participation in the study, then his/her enrollment/randomization code cannot be reused.

3.3.1 Procedures for randomization

Patients who meet all study requirements based on inclusion and exclusion criteria will be centrally randomized (ie, not at the site level or not in a block-stratified fashion) to 1 of 3 treatment groups in a 1:1:1 ratio at Visit 3 (Randomization visit) by the IVRS/IWRS:

- EQW 2 mg + dapagliflozin 10 mg
- EQW 2 mg + placebo
- Dapagliflozin 10 mg + placebo.

Randomization will be stratified by baseline HbA1c stratum ($<9.0\%$ or $\geq 9.0\%$) (refer to Section 3.5); the randomization schedule will be generated according to the stratifying factor. Randomization codes will be assigned strictly sequentially as patients become eligible for randomization.

Specific information concerning the use of the IVRS/IWRS will be provided to the investigators. If a patient is discontinued from the study, his/her randomization or enrollment number will not be reused, and the patient will not be allowed to re-enter the study. Randomized patients who discontinue early from the study will not be replaced.

If a randomization number is allocated incorrectly, no attempt should be made to remedy the error once study material has been dispensed. The patient will continue with the allocated number and study material. AstraZeneca or representative should be notified as soon as the error is discovered. Subsequent patients will continue using the first unallocated randomization number in the original numbering sequence.

3.4 Procedures for handling incorrectly enrolled or randomized subjects

Patients who fail to meet the eligibility criteria should not, under any circumstances, be enrolled or receive study medication. There can be no exceptions to this rule. Patients who are screened, but subsequently found not to meet all the eligibility criteria must not be randomized or initiated on treatment, and must be withdrawn from the study.

Where a patient does not meet all the eligibility criteria but is randomized in error, or incorrectly started on treatment, the investigator should inform the study physician immediately, and a discussion should occur between the study physician and the investigator regarding whether to continue or discontinue the patient from treatment. The study physician must ensure all decisions are appropriately documented.

3.5 Methods for assigning treatment groups

Patients who meet all criteria for this study will be randomized to double-blinded treatment at Visit 3. Assignment to treatment groups will be determined by a computer-generated random sequence using an IVRS. Random assignment to study treatment will be stratified by HbA1c stratum ($<9.0\%$ or $\geq 9.0\%$) based on the HbA1c (%) value of individual patients that was measured at a visit immediately preceding the randomization visit (which is Visit 2 at Week -1 in this study) and is available at the time of randomization. However, throughout the protocol, this is referred to as the baseline HbA1c stratum.

3.6 Methods for ensuring blinding

During the Lead-in Period, patients will be treated with single-blinded placebo (tablets and injection). Patients, the investigator, study site personnel, and Sponsor personnel involved with data review and analysis will be blinded starting at Visit 3 (randomization), and will remain blinded to study treatment throughout the 28-week randomized treatment period. Only patients and investigators will remain blinded during the 24-week extension period. To preserve the blinding, access to the treatment codes will be limited to personnel not involved in the daily conduct of the trial or data review and analysis.

No member of the study team in AstraZeneca, at study sites, or any contract research organization (CRO) handling data will have access to the randomization scheme during the conduct of the study with the exception of AstraZeneca's Investigational Product Services and Patient Safety.

The randomization schedule for blinding of randomized treatment will be maintained by AstraZeneca or representative and will not be disclosed until after the first database lock at the end of the initial 28-week treatment period. AstraZeneca and its applicable representative(s) will be unblinded in Extension Periods 1 and 2 (ie, from Week 28 onwards). Sites and patients will remain blinded during Extension Periods 1 and 2.

The results for FPG, HbA1c, urine glucose/creatinine ratio, urine glucose, and urine creatinine are blinded to the investigator for all visits except Visits 1 to 3. FPG and HbA1c values are

blinded to the investigator site until the unblinding criteria for rescue therapy are met. Once the criteria are met, fasting plasma glucose and HbA1c will be reported to the site for an individual patient (ie, if FPG >270 mg/dL from Week 8 to Week 12 [excluding Week 12], or FPG >240 mg/dL from Week 12 to Week 20 [excluding Week 20], or FPG >200 mg/dL from Week 20 to Week 28 [including Week 28]). Previous values will remain blinded and the site will only receive the values going forward from the point the criteria were met.

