Study duration will be at least 116 weeks, including a 1-week screening period, a 1-week placebo lead-in period, a 28-week double-blind treatment period, a 24-week double-blind extension period (Extension Period 1), an additional 52-week double-blind extension period (Extension Period 2), and a 10-week safety follow-up period.

Investigational product, dosage and mode of administration

Exenatide once weekly and matching placebo:

Exenatide once weekly or matching placebo will be administered using a 2-mg vial with adaptor, a syringe containing diluent, and a 23-Gauge x 5/16 inch needle. Doses of EQW or matching placebo are to be administered by subcutaneous (SC) injection in the abdomen, thigh, or upper arm once weekly for the 28-week double-blind treatment period and for Extension Periods 1 and 2.

Dapagliflozin and matching placebo:

Dapagliflozin 10 mg tablets or matching placebo will be administered orally once daily for the 28-week double-blind treatment period and for Extension Periods 1 and 2.

Other Treatments

Metformin:

Up to Visit 20 (Week 114), patients should continue to administer the same type and dose of metformin therapy they were using at study entry. Metformin should be administered and stored according to product and country specific labelling.

Rescue therapy:

Patients who require rescue therapy will receive open-label titrated basal insulin.

Statistical methods

Populations for analyses

There will be 2 analysis sets for the efficacy evaluation:

- Intent-to-treat (ITT), the primary analysis set, will include randomized patients who receive at least 1 dose of study medication and have at least 1 post-baseline HbA1c assessment.
- Per-protocol (PP), the secondary analysis set, will be a subset of the ITT population through the exclusion of those with important protocol violation(s). Important protocol violations are those that have the potential to affect the result of the primary analysis. Detailed exclusion criteria for the PP population will be specified in the SAP. Patients excluded from the PP analysis will be identified before database lock.

All randomized patients receiving at least 1 dose of study treatment will be considered in the safety population and included in the safety analysis.

Sample size estimation

A total of 209 patients per treatment group are required, assuming:

- Mean difference of 0.35% in HbA1c change from baseline with EQW + dapagliflozin versus each monotherapy

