3.8 Restrictions

Once screened and qualified for entry, patients will be instructed as follows:

- Any new prescription medications or over the counter preparations must be reported to study site staff. For restrictions on concomitant medications, refer to Sections [3.1](#) and [3.2](#).
- Continue metformin therapy at current dosage and at approximately the same time each day, except that any morning dose of metformin should be delayed on the morning of study-site visits.

- Fast overnight for at least 8 hours prior to each study-site visit, ie, no food or beverage except water.
- Withhold alcohol, tobacco, and caffeine and refrain from intense exercise 24 hours prior to each study-site visit.
- Do not do nate blood for the duration of the study.
- Delay administering the morning dose of metformin therapy (if applicable) and study medication (as applicable) on the morning of each study-site visit and bring metformin and study medication to each study-site visit.
- Patients should not be prescribed GLP-1 receptor agonists (BYETTA, BYDUREON, or Victoza[®]) or SGLT-2 inhibitors (Farxiga, Forxiga, or Invokana), or any other GLP-1 analogues or SGLT2 inhibitors during the 10-week safety follow-up period.

The Sponsor or designee should be contacted if the investigator is informed of any restriction violations. The Sponsor will decide whether a patient with restriction violations will be allowed to continue study participation.

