3.9 Discontinuation of investigational product

Patients may be discontinued from the study medication in the following situations:

- Patient decision. The patient is at any time free to discontinue treatment, without prejudice to further treatment.
- Patient experiences an AE that, in the investigator's opinion, necessitates discontinuation from study medication.
- The investigator decides that the patient should discontinue study medication. If this decision is made because of a serious adverse event (SAE) or a clinically significant abnormal laboratory value, appropriate measures are to be taken. The Sponsor or its designee is to be alerted immediately. Refer to Section 6.4, Reporting of SAEs.
- Severe non-compliance with the study protocol.
- Calculated creatinine clearance <45 mL/min confirmed by repeat testing or a decrease in renal function that would preclude continued treatment with metformin according to local guidance.
- Loss of glucose control. If any patient experiences a loss of glucose control, in addition to study medication, the investigator should initiate rescue therapy and the patient may continue study participation. The

investigator should follow local prescribing information for the rescue therapy and may discuss appropriate rescue therapy with the AstraZeneca Medical Monitor if needed. Patients must first complete the Rescue visit procedures before receiving open-label rescue therapy. Rescued patients with central laboratory HbA1c values $>8.0\%$ despite a maximum tolerated dose of rescue therapy for 12 weeks will be discontinued from the study and referred for additional anti-hyperglycemic therapy (see Section 4.2).

- Patients with a central laboratory ALT and/or AST $>3x$ ULN will be scheduled for a follow-up visit within 3 days following the receipt of the result (see Appendix C, “Algorithm on Management of Sustained Elevated Liver Safety Abnormalities”). Patients should be discontinued from study medication if the initial and repeat laboratory tests meet any of the following criteria:
 - ALT and/or AST are $>3x$ ULN **and** TB $>2x$ ULN.
 - ALT and/or AST are $>5x$ ULN for ≥ 14 consecutive days, at any time after initial confirmatory results.
 - ALT and /or AST are $>8x$ ULN.

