3.9.1 Procedures for discontinuation of a patient from investigational product

If deemed necessary by the investigator, study medication can be stopped temporarily and then re-started after discussion with the medical monitor. These situations will be handled on a case by case basis and all decisions will be documented in the patient’s study file.

At any time, patients are free to discontinue study medication or withdraw from the study (ie, study medication and assessments – see Section 3.10), without prejudice to further treatment. A patient that decides to discontinue study medication will always be asked about the reason(s) and the presence of any AEs. AEs will be followed up (see Section 6); patient diaries and all study medications should be returned by the patient.

Patients who discontinue permanently from the study medication will have an Early Termination Visit equivalent to the Week 28 assessments at the time of study medication discontinuation (see Section 4.2.2). Discontinued patients will then be contacted via telephone according to the visit schedule in the Study Plan (Table 1 and Table 2), ie, during the time windows during which the scheduled clinic visits would have been conducted. At these contacts, the following data will be collected and entered onto the clinical database:

- Concomitant medication
- AEs

Discontinued patients should return to the study site and complete assessments required for Visit 12 (Week 28), Visit 15 (Week 52), and Visit 19 (Week 104) as appropriate and outlined in the Study Plan ([Table 1](#) and [Table 2](#)). These patients will also be contacted via telephone according to the visit schedule in the Study Plan ([Table 1](#) and [Table 2](#)).

Discontinued patients should also return to the study site to complete the Follow-up visit (Visit 20) 10 weeks after the Visit 19 (Week 104) assessments.

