4.3 Extension Period 1 (24-week Extension period)

Patients will return for follow-up visits every 8 weeks during the long-term site-and patient-blinded Extension Period 1. Patients will monitor their fasting blood glucose levels at least once a week and will continue to enter the results into the patient diary. Diet and lifestyle modification will be reinforced at each visit during this period. Patients will be contacted approximately monthly between visits (as described in [Table 2](#)).

The need for initiation of rescue therapy will be assessed based on criteria in [Table 4](#). Patients must first complete the Rescue visit procedures before receiving open-label rescue therapy.

Table 4 **Criteria for initiation of rescue therapy during Extension Period 1**

Period	Central Laboratory HbA1c
From the day of Visit 13/Week 36 up to and including Visit 15/Week 52 and all unscheduled visits through the day prior to Visit 16/Week 65	HbA1c >8.0%

Note: Rescue upon receipt of HbA1c results. No repeat testing required for confirmation.

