8. STATISTICAL ANALYSES BY ASTRAZENECA

8.1 Statistical considerations

All personnel involved with the analysis of the study will remain blinded until database lock and protocol violators identified at the end of the 28-week randomized treatment period. AstraZeneca and its applicable representative(s) will be unblinded in Extension Periods 1 and 2 (ie, from Week 28 onwards). Sites, site monitors, and patients will remain blinded during Extension Periods 1 and 2.

Statistical analysis of this study will be the responsibility of AstraZeneca or its representatives.

All of the data will be entered, verified, and archived by AstraZeneca or its representatives. All data listings, summaries, and analyses will be performed under the guidance and approval of statisticians at AstraZeneca.

Baseline: Baseline refers to the last measurement collected prior to the first dose of study medication at the randomization visit.

All collected data will be listed. A detailed statistical analysis plan (SAP) will be written and approved prior to database lock.

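### Sponsor unblinding in the extensions conflicts with other blinding text in Sections 3.6 and 3.7, and no text keeps sponsor-side staff who advise on individual patients blinded

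*Protocol*

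**What the plan says.** **Unblinding rule.** Sections 3.6 and 8.1 both say: "AstraZeneca and its applicable representative(s) will be unblinded in Extension Periods 1 and 2 (ie, from Week 28 onwards". Section 8.1 adds: "Sites, site monitors, and patients will remain blinded during Extension Periods 1 and 2". Section 3.6 gives two lists of who stays blinded. One covers patients and investigators, for the 24-week extension; the other covers sites and patients, for both extensions. Neither mentions site monitors.

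**Other blinding text.** Section 3.6 limits treatment codes to people outside daily conduct, data review and analysis. It withholds the randomization scheme from the sponsor's study team, the sites and any CRO handling data while the study is conducted, except for Investigational Product Services and Patient Safety. It also says the schedule is not disclosed before the first database lock. Section 3.7 allows no code break for planned analyses until evaluability decisions are documented for each patient, and holds allocation information securely until the study ends.

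**Labels.** The synopsis (Duration of treatment) lists "a 24-week double-blind extension period (Extension Period 1), an additional 52-week double-blind extension period (Extension Period 2". Section 4.3 instead describes a "long-term site-and patient-blinded Extension Period 1", and Section 4.4 labels Extension Period 2 the same way.

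**Sponsor-side roles, none limited to the first 28 weeks.**
- Section 3.8: "The Sponsor will decide whether a patient with restriction violations will be allowed to continue study participation".
- Section 3.9.1: "study medication can be stopped temporarily and then re-started after discussion with the medical monitor".
- Section 3.9: on loss of glucose control, the investigator "may discuss appropriate rescue therapy with the AstraZeneca Medical Monitor if needed".
- Section 5.2.1.4: continuation after a persistent calcitonin elevation is discussed with the medical monitor.

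**The concern.** Section 1.2 gives long-term safety and durability as the purpose of the extensions. Their outcomes (Sections 2.5 and 2.6) include adverse event incidence and the proportion rescued or discontinued for lack of glycemic control. Someone who knows the arm and has a say in whether a patient continues or restarts drug, or in how an event is queried or coded, can influence those outcomes without intending to. Section 3.6 appears designed to prevent this by separating code holders from study conduct. The unblinding sentence removes that separation without saying which sponsor roles it covers. As a result, two teams could follow the protocol in good faith and give the codes to different people.

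**Working it through.** The plan states no figure on this point, so the check is a comparison of passages, followed by a bound on exposure.

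**1. Can the blinding statements all be followed?**

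| Question | One statement | Another statement |
|---|---|---|
| Who on the sponsor side may know the arm during the study? | 3.6 and 8.1: the sponsor and its applicable representatives, throughout the extensions | 3.6: no study-team member and no data-handling CRO, apart from two functions |
| From when? | 3.6 and 8.1: Week 28 | 3.6: after the first lock; 3.7: allocation kept secure until study end |
| Before or after evaluability decisions? | 3.6 and 8.1: codes open during the extensions | 3.7: closed for planned analyses until each patient's evaluability is settled |

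The third row matters because Section 8.5.7 also plans analyses after Extension Periods 1 and 2. Evaluability decisions on data not yet collected at the Week 28 lock must come after that unblinding, so the Section 3.7 rule cannot be met for those analyses as written.

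**2. Which sponsor-side roles touch individual patients or data after Week 28?**
- Decision: continuation after restriction violations (3.8).
- Consultation: restart after a temporary stop (3.9.1) and continuation after raised calcitonin (5.2.1.4).
- Optional advice: rescue therapy (3.9).
- Data handling: adverse event coding and manual queries by the CRO (9.4).

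Section 8.1 names site monitors as remaining blinded. No sentence does the same for the medical monitor, data management or medical coding in the extensions.

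**3. How many treatment weeks could be exposed?**
Upper limit, if codes opened at a patient's own Week 28: 104 − 28 = 76 weeks, and 76/104 = 73%.

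Under the lock rule, disclosure is a single calendar event after the last patient's Week 28 (3.6, 8.5.7). Inputs are the planned dates in the synopsis and Section 9.3: first patient enrolled 3Q 2014, study complete 4Q 2017. Two assumptions are needed: completion means the Week 114 visit (798 days after randomization), and enrollment means screening, 14 days before randomization.
- Last patient randomized: 1 October to 31 December 2017 minus 798 days = 26 July to 25 October 2015.
- Last patient's Week 28: plus 196 days = 7 February to 8 May 2016.
- First patient randomized: 1 July to 30 September 2014 plus 14 days = 15 July to 14 October 2014.
- First patient's position when the last reaches Week 28: shortest interval, 14 October 2014 to 7 February 2016, is 481 days or about Week 69. Longest, 15 July 2014 to 8 May 2016, is 663 days or about Week 95.
- First patient's remaining treatment weeks: 104 − 95 = 9 to 104 − 69 = 35.

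On these planned dates, exposure runs from about 9 to 35 weeks for the first patient to at most 76 for the last, less in each case by the time taken to reach the lock. The earliest patients pass Week 52 before any disclosure.

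**The case against.** The strongest reply is that this is an openly disclosed and limited design choice. Patients, sites and site monitors stay blinded, and Sections 4.3 and 4.4 give the exact level of blinding, so the synopsis label is loose rather than false. HbA1c is a central-laboratory measure. Rescue in the extensions follows fixed HbA1c thresholds (Tables 4 and 5), and the investigator prescribes it. Cardiovascular and hepatic events are adjudicated by blinded committees (6.8.1, 6.8.2). All extension efficacy endpoints are exploratory (8.4.4, 8.4.5). All of this stands, and it limits what is at stake.

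A reader might infer several stronger points that the document does not support:
- *The extensions become open-label for 73% of treatment, affecting every Week 52 and Week 104 outcome.* Sites and patients remain blinded, and the lock sentence makes 73% an upper limit.
- *The medical monitor and the CRO's coding staff are unblinded.* This is an inference. Only applicable representatives are unblinded, and another sentence in Section 3.6 excludes a data-handling CRO. The defect is that the text does not settle the matter.
- *The sponsor decides on restart and rescue.* Only Section 3.8 gives it a decision. Restart and calcitonin are discussions, and rescue advice is optional.
- *Unblinding could precede the primary lock.* Starting at Week 28 permits that reading patient by patient, but the lock sentence contradicts it.

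The reply does not answer the conflict among Sections 3.6, 3.7 and 8.1, or the missing statement that those advising on individual patients stay blinded.

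**Conclusion.** The point holds as a conflict in the blinding rules and an avoidable gap in the separation of roles. The protocol does not say consistently who on the sponsor side may know treatment during the extensions, or from when, and it leaves one sponsor decision and several medical-monitor consultations without stated blinding. The consequence is a possible bias in exploratory 52- and 104-week continuation and adverse event outcomes. No direction or size can be derived from the document, and none is claimed; it would be too strong to say that the long-term objectives are undermined. The conclusion about Week 28 rests on disclosure actually waiting for the first database lock. The exposure range rests on the planned dates and the two assumptions stated with it. The change is worth making because it is cheap and restores the separation that Section 3.6 already describes.

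**What to change.** 1. Reconcile Sections 3.6, 3.7 and 8.1, so that one rule states who holds the codes in each period and how the evaluability condition in Section 3.7 applies to the Week 52 and Week 104 analyses.
2. Replace the Week 28 start with: *after the first database lock, when all patients have completed Week 28.*
3. Replace the general unblinding with: *only a named reporting team, in addition to the exceptions already listed, is unblinded at that point.*
4. Add: *the medical monitor, data management, medical coding, and sponsor staff who decide or advise on individual patients or on evaluability stay blinded until the final database lock.*
5. Describe both extensions as site- and patient-blinded throughout, including the synopsis, and use one list of who stays blinded.

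The cost is protocol and blinding-plan wording plus access control on the Week 28 outputs, with no added patients or procedures. The small downside is that the unblinded reporting team must be kept apart from ongoing study conduct.
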